7. Statistical Analysis	32
7.1 Sample-Size Determination	32
7.2 Analysis Sets.....	33
7.3 Analysis Plan	33
7.3.1 Statistical Hypothesis	33
7.3.2 General principles	33
7.3.3 Study Disposition and Participant Flow	34
7.3.4 Demographics and Baseline Characteristics	34
7.3.5 Medication Adherence.....	34
7.3.6 Efficacy Analyses	34
7.3.7 Safety Analysis.....	34
7.3.8 Multiplicity Adjustment	35
7.3.9 Handling of Missing Data	35
8. Safety Evaluation	36
8.1 Definitions	36
8.1.1 AEs	36
8.1.2 Serious Adverse Events (SAEs)	36
8.2 AE Assessment	37
8.2.1 Seriousness	37
8.2.2 Severity Grading	37
8.2.3 Causality.....	38

8.2.4 Measures taken with Regard to Study Treatment	39
8.2.6 Outcome	41
8.3 AE Reporting	41
8.4 Observation and Management of Special Adverse Events	42
9. Ethical Principles and Requirements for Clinical Research	46
9.1 Ethical Standards	46
9.2 Ethics Committee	47
9.3 Informed Consent	47
9.3.1 Informed Consent Process and Documentation	48
9.3.2 Confidentiality of Participant Information	48
10. Data Management and Quality Control	48
10.1 Data Management.....	48
10.2 Monitoring	51
11. Study Management	51
11.1 Quality Control and Quality Assurance	51
12. Responsibilities of All Parties and Other Relevant Provisions.....	52
12.1 Responsibilities of the Lead Study Institution.....	52
12.2 Responsibilities of Clinical Research Sites (Study Centers)	53
13. Reference	55

Abstract of the Research Program

[figure not shown]
Title	Efficacy and safety of memantine in the treatment of patients with frequent symptomatic atrial premature beats: a multicenter, randomized, double-blind, placebo-controlled study (STOP-AP)
Objective	MAIN OBJECTIVE: To evaluate the effectiveness of memantine in the treatment of frequent symptomatic atrial premature beats. SECONDARY OBJECTIVE: To evaluate the safety of memantine in the treatment of frequent symptomatic atrial premature beats.
Principal Investigator and Lead Institution	[name], Shanghai East Hospital, Tongji University.
Sample Size	A total of 256 patients with frequent symptomatic atrial premature beats are to be recruited.
Inclusion Criteria	
(1) Age: 18 to 80 years, inclusive.
 
(2) Symptomatic premature atrial contractions (PACs): Documented at screening as \geq 1,000 PACs during a 24-hour ambulatory electrocardiogram (ECG) recording.
 
(3) Informed consent: Ability and willingness to understand and comply with all study procedures and to sign the written informed-consent form before any protocol-specific activities are performed.

Exclusion criteria	
(1) Atrial or ventricular arrhythmias Atrial fibrillation (AF), atrial flutter (AFL), or sustained atrial tachycardia (SAT) documented by 12-lead ECG within 6 months before screening or detected on the baseline 72-hour patch-type ambulatory ECG; Ventricular tachycardia (excluding brief nocturnal runs) or ventricular fibrillation.
 
(2) Recent cerebrovascular or cardiac events Ischemic or hemorrhagic stroke, or transient ischemic attack, within 6 months before screening; Cardiac surgery, myocardial infarction, percutaneous coronary intervention, or catheter ablation for atrial arrhythmias within 3 months before screening.
 
(3) Severe cardiac dysfunction Left-ventricular ejection fraction \leq 40 %; New York Heart Association class III or IV heart failure.
 
(4) Clinically significant conduction disease Sick-sinus syndrome without a permanent pacemaker; Second-degree type II or higher atrioventricular block, or bifascicular block.
 
(5) Recent antiarrhythmic therapy

	
Amiodarone within 4 weeks before screening; Any other antiarrhythmic agent—including herbal preparations with antiarrhythmic properties—within 1 week before screening.
 
(6) Other serious cardiac conditions
 
Unstable angina, severe congenital heart disease (except patent foramen ovale), prior prosthetic heart-valve replacement, acute myocarditis or endocarditis, rheumatic valvular disease, or hypertrophic obstructive cardiomyopathy.
 
(7) Limited life expectancy
 
Any comorbid condition with an anticipated survival of < 1 year.
 
(8) Hepatic impairment
 
Active hepatitis or clinically significant liver dysfunction (ALT or AST > 3 × ULN, or total bilirubin > 3 × ULN).
 
(9) Renal impairment
 
Estimated glomerular filtration rate < 40 mL · min⁻¹ · 1.73 m⁻² (CKD-EPI formula).
 
(10) Concurrent investigational therapy
 
Use of any investigational drug or device within 1 month—or five elimination half-lives, whichever is longer—before screening.
 
(11) Pregnancy or lactation
 
Pregnant or breastfeeding women, or a positive serum pregnancy test before randomization.
 
(12) Metabolic, surgical, or pulmonary instability
 
Uncontrolled hyperthyroidism; Perioperative cardiothoracic surgery — defined as the interval from 1 week before to 2 weeks after the procedure; Uncorrected electrolyte imbalance (serum potassium > 5.5 mmol/L or < 3.5 mmol/L; serum magnesium < 1.5 mmol/L); Chronic obstructive pulmonary disease with respiratory failure or active, uncontrolled infection.
 
(13) Neurologic or psychiatric disorders
 
History of epilepsy, seizures, or psychiatric illness that could interfere with study participation.
 
(14) Drug hypersensitivity
 
Known allergy to memantine hydrochloride or any excipient of the study drug.
 
(15) Current memantine therapy
 
Ongoing treatment with memantine for moderate-to-severe Alzheimer's disease.
 
(16) Other contraindications
 
Any condition that, in the investigator's judgment, makes the participant unsuitable for enrollment in the study.

--	--

Research Design	This study is a multicenter, randomized, double-blind, parallel-group, placebo-controlled superiority trial.
Efficacy Endpoints	
Primary Efficacy Endpoint: The percentage change from baseline in the 24-hour mean number of PACs at Week 6.
 
Secondary Efficacy Endpoints:
 
 a) The change from baseline in the 24-hour mean number and burden of PACs at Weeks 4, 6, and 8; b) The change from baseline in the 24-hour mean episode count and burden of non-sustained atrial tachycardia (NSAT) at Weeks 4, 6, and 8; c) The change from baseline in the 24-hour mean episode count of SAT, AF, and AFL at Weeks 4, 6, and 8; d) The proportion of participants with new-onset SAT, AF, or AFL lasting ≥ 30 seconds during a continuous 72-hour monitoring period at Weeks 4, 6, and 8. This endpoint will be calculated based on the first occurrence of SAT, AF, or AFL during the respective 72-hour monitoring windows; e) The cumulative incidence of new-onset AF from baseline to Week 8: The proportion of participants who experience their first episode of AF lasting ≥ 30 seconds during any of the 4th, 6th, or 8th-week follow-up windows, with each participant counted only once, even if they have multiple occurrences across different follow-up windows; f) The change from baseline in the SF-36 quality of life score at Week 6; g) Efficacy analysis of PACs or NSAT, based on the proportion of responders.
Safety Endpoints	The incidence of adverse events (including psychiatric symptoms, seizures, bradycardia, new-onset heart failure, etc.), serious adverse events, laboratory test abnormalities, and abnormal electrocardiogram findings.
Study Overview	
This is a multicenter, randomized, double-blind, parallel-group, placebo-controlled superiority trial aimed at enrolling 256 patients aged 18 to 80 years with frequent symptomatic PACs.
 
Eligible patients, following initial screening, will undergo 72-hour continuous ambulatory ECG monitoring to establish baseline PAC counts. Based on the monitoring data, eligibility will be confirmed. Qualified participants will then be randomly assigned in a 1:1 ratio on Day 0 to either the memantine group or the placebo group. A total of 256 participants will be enrolled, with 128 in each group.

Stratification factors will include age (≥ 65 years vs. < 65 years) and baseline PAC count (≥ 5000 per 24 hours vs. < 5000 per 24 hours).

The study is comprised of a screening period (≤ 14 days), a treatment period (Day 42 ± 3 days), and a follow-up period (Day 56 ± 3 days). The study design is presented in the figure below.

Notes:

- The drug administration period for this study spans from Day 42 to Day 45. The 72-hour ambulatory ECG monitoring at visits V3, V4, and V5 is scheduled to begin on Day 25 to Day 28 for V3, Day 39 to Day 42 for V4, and Day 53 to Day 56 for V5. For the V4 visit, the ECG monitoring must commence 3 days prior to the end of the administration period. For example, if drug administration concludes on Day 42, the 72-hour ambulatory ECG monitoring must begin on Day 39. Should the monitoring occur on Day 42, drug administration must continue until Day 45.
- All other procedures at visits V3 to V5 should be performed between the initiation and removal of the 72-hour ambulatory ECG monitoring device.

The memantine group: participants will receive memantine according to the following regimen:

Week 1: $\frac{1}{2}$ tablet per dose (5 mg per dose), twice daily, to be taken at the same time each morning and evening (with a recommended dosing interval of 12 hours \pm 2 hours).

Weeks 2 to 6: 1 tablet per dose (10 mg per dose), twice daily, to be taken at the same time each morning and evening (with a recommended dosing interval of 12 hours \pm 2 hours).

	
The placebo group: participants will receive placebo tablets according to the following regimen:
 
Week 1: $\frac{1}{2}$ tablet per dose, twice daily, to be taken at the same time each morning and evening (with a recommended dosing interval of 12 hours \pm 2 hours).
 
Weeks 2 to 6: 1 tablet per dose, twice daily, to be taken at the same time each morning and evening (with a recommended dosing interval of 12 hours \pm 2 hours).
 
Duration of administration
 
The duration of drug administration in this study will be from Day 42 to Day 45.

Prohibited Medications	
The following medications are prohibited throughout the study period:
 
 N-Methyl-D-Aspartate receptor (NMDA) antagonists, including amantadine, ketamine, dextromethorphan, and others. Levodopa, dopamine receptor agonists, anticholinergic agents, and barbiturates. Class I, II, III, and IV antiarrhythmic drugs, as well as other herbal medicines and/or traditional Chinese medicines with antiarrhythmic properties (except in cases where participants are unable to tolerate these medications due to severe symptoms). Antispasmodic agents, including dantrolene, baclofen, and others. Other medications that, in the investigator's judgment, may interfere with the efficacy or safety assessments.
Calculation of Sample size	
Based on the results of our preliminary exploratory single-arm study evaluating the efficacy of memantine in the treatment of PACs, the 24-hour mean reduction in PACs was 75.4%. Considering the robustness of results from the small-sample trial and potential sampling error, we conservatively estimated a 50% reduction in the 24-hour mean burden of PACs following treatment with memantine, while the placebo group is expected to show a 30% reduction, with a standard deviation of 35%. The dropout rate is assumed to be 15.0%. Using EAST 6.5 software for sample size calculation with a one-sided $\alpha = 0.025$ and a 1:1 allocation ratio between the memantine and placebo groups, a total of 256 participants will be enrolled, providing more than 95% power to detect the pre-specified between-group difference.

Statistical Analysis	
General Principle
 
For continuous data, statistical descriptions will include the number of cases, mean, standard deviation, median, minimum, and maximum.
 
For categorical data, statistical descriptions will include the number and percentage of cases. Percentages will be calculated using the number of participants in the corresponding group as the denominator, unless otherwise specified.
 
Efficacy Analysis

	
The difference between the two groups for the primary endpoint will be assessed by calculating the mean difference in the percentage reduction of 24-hour mean PACs at Week 6 between the memantine and placebo groups, along with its 95% confidence interval (CI).
 
For key secondary efficacy endpoints, hypothesis testing will be conducted using a fixed-sequence approach, while other secondary endpoints will be analyzed using descriptive statistics.
 
Safety Analysis
 
All adverse events will be coded using the Medical Dictionary for Regulatory Activities (MedDRA), categorized by System Organ Class (SOC) and Preferred Term (PT).
 
The number and incidence rate of adverse events (AEs), serious adverse events (SAEs), and AEs leading to death will be summarized. AEs, SAEs, and those resulting in death will also be summarized by SOC and PT, with the corresponding number of cases and incidence rates reported.

--	---

1. Background

The incidence of PACs increases with age [1,2]. Previously, PACs were considered benign arrhythmias with minimal clinical significance. However, recent studies have shown that frequent PACs may indicate subclinical cardiovascular disease. After adjusting for multiple variables, patients with frequent PACs have a 2- to 4-fold increased risk of developing AF, a 2- to nearly 3-fold increased risk of first stroke, a 39% to 100% increased risk of all-cause mortality, and a 74% increased risk of coronary artery disease [3].

The association between frequent PACs and AF, stroke, and mortality may be mediated by three distinct mechanisms: First, frequent PACs are more likely to progress to subclinical AF, which in turn increases the risk of stroke and death. Second, PACs are associated with traditional cardiovascular risk factors. Third, frequent PACs may indicate atrial cardiomyopathy, a condition characterized by electrophysiological abnormalities and a hypercoagulable state, which may still lead to thrombus formation in sinus rhythm, thus increasing stroke risk [1-2,4]. The growing recognition of the potential risks associated with frequent PACs has prompted clinicians to reconsider their clinical significance, suggesting that they should no longer be regarded as a benign condition.

The European Heart Rhythm Association (EHRA) consensus on the management of asymptomatic arrhythmias recommends monitoring rhythm, addressing cardiovascular risk factors, and assessing for structural heart disease in patients with frequent PACs. For patients with >500 PACs/24 hours or any continuous episode of more than 20 PACs, especially if brief episodes of AF are observed, individualized anticoagulation therapy should be considered [5]. However, due to the lack of clinical evidence supporting antiarrhythmic drug treatment for PACs, the consensus does not recommend pharmacological therapy. Limited evidence from previous studies suggests that for patients with persistent symptomatic PACs, after minimizing potential triggers (e.g., smoking, caffeine, alcohol, stress), β -blockers may be used to reduce PAC frequency and associated symptoms, provided there are no contraindications. However, the effectiveness of β -blockers is uncertain and varies among patients. A cohort study

investigating the use of low-dose β -blockers to improve the long-term prognosis of PAC patients found that, after propensity score matching, mortality was significantly lower in the treated group in the high-load subgroup (≥ 100 PACs/day) over a mean follow-up of approximately three years, although the incidence of new-onset stroke and AF was similar between groups^[6]. Class IA, IC, and III antiarrhythmic drugs have been shown to reduce the frequency of symptomatic PACs and suppress arrhythmias such as AF, AFL, and atrioventricular reentrant tachycardia^[7-9]. However, these drugs have not been subjected to controlled studies, and their use must be carefully weighed against the potential risk of pro-arrhythmia. Furthermore, digoxin, calcium channel blockers, and class IB antiarrhythmic drugs have not shown clear benefits in patients with symptomatic PACs. Therefore, there is an urgent need to develop novel drugs for the treatment of PACs and conduct prospective studies on antiarrhythmic therapies.

The glutamate neurotransmitter system is a crucial signaling pathway that regulates the excitability and conduction of neurons. Similarly, myocardial cells, as excitable cells, also exhibit excitability and conduction properties. [name]'s team first discovered that rat atrial myocardial cells have an intrinsic, rich glutamatergic neurotransmitter system, which regulates myocardial cell excitability and conduction by controlling ionotropic glutamate receptors (iGluRs). Under resting potential, activation of glutamate receptors in rat atrial muscle cells induces transient inward currents, facilitating the generation of action potentials, thus increasing cell excitability and conduction. Importantly, specific glutamate receptor inhibitors block this effect. Furthermore, a similar glutamatergic system with electrophysiological regulatory functions has been identified in human atrial myocardial cells^[10,11].

Memantine (Mem) is a voltage-dependent, non-competitive N-methyl-D-aspartate (NMDA) receptor antagonist that inhibits the activity of ionotropic glutamate receptors (iGluRs)^[12]. It is used as a first-line treatment for moderate to severe Alzheimer's disease, with a good safety profile and patient tolerance^[13]. Notably, preclinical studies conducted by [name]'s team have shown that memantine effectively reduces the incidence of AF induced by three different pathophysiological conditions (stretch-induced, cholinergic, and ischemic AF) in isolated rat hearts in a concentration-

dependent manner. In *in vivo* experiments, memantine effectively prevented and terminated AF induced by three different pathophysiological conditions (aortic constriction, acetylcholine, and hypoxia) in rats. The primary mechanism of action is that memantine blocks glutamate currents in atrial myocardial cells, reducing calcium leakage, and effectively reducing trigger activity, delayed afterdepolarization, and ectopic beats, thereby reducing AF triggers and effectively preventing AF. Additionally, memantine significantly decreased the number of reentrant circuits in the atrial myocardium, thus effectively terminating AF. Furthermore, memantine was shown to reduce the incidence of AF-like abnormal electrophysiological events and delayed afterdepolarization in human-induced pluripotent stem cell-derived atrial myocardial cells (iPSC ACMs), suggesting that this drug may also exert electrophysiological regulatory effects on human myocardial cells. Previous animal and clinical studies have demonstrated that memantine has a favorable safety profile, reducing the occurrence of reperfusion arrhythmias and slowing heart rate without prolonging the QT interval [15-17], thus not increasing the risk of torsades de pointes. Based on these findings, we hypothesize that memantine may be an ideal treatment for rapid atrial arrhythmias. The repurposing of an existing drug significantly shortens the drug development timeline and reduces research costs. Therefore, this study aims to explore the efficacy and safety of memantine in patients with frequent PACs.

2. Study Objectives and Endpoints

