4.2 Exclusion Criteria

(1) Atrial or ventricular arrhythmias

AF, AFL, or SAT documented by 12-lead ECG within 6 months before screening or detected on the baseline 72-hour patch-type ambulatory ECG;

Ventricular tachycardia (excluding brief nocturnal runs) or ventricular fibrillation.

(2) Recent cerebrovascular or cardiac events

Ischemic or hemorrhagic stroke, or transient ischemic attack, within 6 months before screening;

Cardiac surgery, myocardial infarction, percutaneous coronary intervention, or catheter ablation for atrial arrhythmias within 3 months before screening.

(3) Severe cardiac dysfunction

Left-ventricular ejection fraction $\leq 40\%$;

New York Heart Association class III or IV heart failure.

(4) Clinically significant conduction disease

Sick-sinus syndrome without a permanent pacemaker.

Second-degree type II or higher atrioventricular block, or bifascicular block.

(5) Recent antiarrhythmic therapy

Amiodarone within 4 weeks before screening;

Any other antiarrhythmic agent—including herbal preparations with antiarrhythmic properties—within 1 week before screening.

f) Other serious cardiac conditions

Unstable angina, severe congenital heart disease (except patent foramen ovale), prior prosthetic heart-valve replacement, acute myocarditis or endocarditis, rheumatic valvular disease, or hypertrophic obstructive cardiomyopathy.

g) Limited life expectancy

Any comorbid condition with an anticipated survival of < 1 year.

h) Hepatic impairment

Active hepatitis or clinically significant liver dysfunction (ALT or AST $> 3 \times$ ULN, or total bilirubin $> 3 \times$ ULN).

i) Renal impairment

Estimated glomerular filtration rate $< 40 \text{ mL} \cdot \text{min}^{-1} \cdot 1.73 \text{ m}^{-2}$ (CKD-EPI formula).

(10) Concurrent investigational therapy

Use of any investigational drug or device within 1 month—or five elimination half-lives, whichever is longer—before screening.

(11) Pregnancy or lactation

Pregnant or breastfeeding women, or a positive serum pregnancy test before randomization.

(12) Metabolic, surgical, or pulmonary instability

Uncontrolled hyperthyroidism.

Perioperative cardiothoracic surgery — defined as the interval from 1 week before to 2 weeks after the procedure;

Uncorrected electrolyte imbalance (serum potassium $> 5.5 \text{ mmol/L}$ or $< 3.5 \text{ mmol/L}$; serum magnesium $< 1.5 \text{ mmol/L}$);

Chronic obstructive pulmonary disease with respiratory failure or active, uncontrolled infection.

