Score 1: Mild symptoms, occasional palpitations that do not affect daily life;

Score 2: Moderate symptoms, frequent palpitations, mildly interfering with daily life;

Score 3: Severe symptoms with persistent palpitations that significantly interfere with daily life;

4. Basic information including height, weight, waist circumference, education level, etc;

5. Past medical history: hemorrhagic/ischemic stroke, transient ischemic attack, myocardial infarction, history of epilepsy or seizures, and psychiatric disorders;

6. History of prior medications: medication use within 4 weeks prior to screening; history of non-drug therapy (including surgery): history of non- drug therapy within 6 months prior to screening; collection of a full history of prior cardiac-related surgery;

7. Vital signs include temperature, blood pressure, pulse, and respiration;

8. Including routine blood, liver function (alanine aminotransferase, glutamic aminotransferase, gamma glutamyl transpeptidase, total bilirubin, direct bilirubin, indirect bilirubin), thyroid function (fT3, fT4, TSH), renal function (creatinine, urea nitrogen or urea, glomerular filtration rate), electrolytes (blood sodium, potassium, magnesium, calcium), blood lipids (total cholesterol, triglyceride, HDL cholesterol, LDL cholesterol ester), fasting blood glucose, glycated hemoglobin, NT-pro BNP (preferred) or BNP.

9. Female subjects of childbearing age should undergo blood or urine HCG test to exclude pregnancy.

10. The duration of drug administration in this study was 42-45 days, and the start time of 3-day (72h) ECG recorder monitoring for V3~V5 visits was D25~D28 for V3, D39~D42 for V4, and D53~D56 for V5, respectively. ECG monitoring for the V4 visit should be started 3 days prior to the end of the drug administration, and the 3 consecutive days (72h) of ECG recorder monitoring should be performed at D39, if the administration of drug was ended at D42. recorder monitoring needs to be performed at D39. If 3 consecutive days (72h) of ECG monitoring is performed at D42, the drug must be administered until D45; other operations for V3~V5 visits are performed from the day of the 3-day ECG monitoring on to the day of the removal of the ECG recorder.

Table 5 Specific requirements for each inspection item

Inspection item	Requirements and observables
vital signs	Temperature, blood pressure, pulse, respiration.

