Statistical Analysis Plan

Efficacy and Safety of Memantine in the Treatment of Patients With Frequent Symptomatic Atrial Premature Beats: A Multicenter, Randomized, Double-Blind, Placebo- Controlled Study (STOP-AP)

Study drug:	Memantine Hydrochloride Tablets
Indications:	Frequent Symptomatic Premature Atrial Contractions
Document Type:	Statistical Analysis Plan
Version:	2.0
Release Date:	July 17, 2025

Document Revision History and Amendment Summary		
Version Number	Effective Date	Revision Summary
1.0	2025-02-14	Statistical Analysis Plan, Version 1.0 — Final
2.0	2025-07-17	
1. Removal of the planned interim analysis. An interim analysis for sample- size re- estimation had been prespecified after 128 participants completed the 6-week follow- up. At the planned interim time point, however, enrollment had already reached nearly 256 participants—the trial’s final target sample size. The Trial Steering Committee reviewed enrollment progress and unanimously resolved to cancel the prespecified interim analysis before unblinding. The trial remained fully blinded throughout, thereby preserving data integrity.
 
2. Addition of secondary endpoints:
 
a) The cumulative incidence of new-onset atrial fibrillation (AF) from baseline to Week 8: The proportion of participants who experience their first episode of AF lasting ≥ 30 seconds during any of the 4th, 6th, or 8th-week follow-up windows, with each participant counted only once, even if they have multiple occurrences across different follow-up windows.b) Efficacy analysis (e.g., $\geq 50\%$ reduction) for premature atrial contractions (PACs) or non- sustained atrial tachycardia (NSAT), based on the proportion of responders. 
3. Introduction of a subgroup analysis stratified by left- atrial diameter.

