2.2 Analysis Sets

- **Full Analysis Set (FAS)** — Includes all randomized participants who receive at least one dose of investigational product; analyzed in the treatment groups to which they were randomly assigned (intention-to-treat principle).
- **Per Protocol Set (PPS)** — Includes all randomized participants who received at least one dose of investigational product, underwent at least one post-baseline efficacy assessment, and had no major protocol deviations that could affect evaluation of the primary efficacy endpoints.
- **Safety Analysis Set (SS)** — Includes all randomized participants who received at least one dose of investigational product; safety endpoints are analyzed according to the treatment actually received.

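### The magnesium limit in exclusion (12) pairs a number and a unit that do not fit together; read literally, it excludes nearly every candidate

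*Protocol*

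**What the plan says.** Exclusion (12) in the Protocol synopsis covers metabolic, surgical and pulmonary instability. One of its items is headed "Uncorrected electrolyte imbalance" and sets two potassium limits, "serum potassium > 5.5 mmol/L or < 3.5 mmol/L", and one magnesium limit, "serum magnesium < 1.5 mmol/L". Protocol section 4.2 (12) repeats the magnesium limit with the same number and unit, so a reading error in one copy of the PDF text is not a plausible explanation.

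Magnesium belongs to the screening laboratory panel. Note 8 to the flow table in Protocol section 6.1 lists "electrolytes (blood sodium, potassium, magnesium, calcium" among the tests, and Table 5 repeats it. Neither place gives a unit or a reference range. No other section gives a different unit, a footnote or a waiver for this limit.

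The planned size is 256: "A total of 256 participants will be enrolled, with 128 in each group". The SAP revision history says that, at the planned interim time point, "enrollment had already reached nearly 256 participants".

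Under SAP section 2.2 and Protocol section 7.2, the per-protocol set (PPS) keeps participants who, among other conditions, "had no major protocol deviations that could affect evaluation of the primary efficacy endpoints". SAP section 4.2 evaluates efficacy in the full analysis set (FAS) and uses the PPS for sensitivity assessments.

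**The concern.** An exclusion for an electrolyte imbalance should separate a small group with abnormal values from the rest. If 1.5 mmol/L lies above almost all ordinary values, the criterion separates nobody, because nearly every candidate meets it.

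Two things follow. First, the written limit cannot have been the working limit at sites that enrolled normally, so the threshold in use is not documented. Protocol section 3.2 plans about 20 hospitals, and note 1 to the flow table accepts outside laboratory results for screening, so practice could differ between sites. Second, anyone who checks eligibility against the Protocol text would have to record a deviation from criterion (12) for nearly every randomised participant. SAP section 4.1.2 requires deviations to be listed and classified by severity before database lock, so the question will have to be settled then in any case.

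**Working it through.** The plan gives no calculation behind this limit, so there is no figure to reproduce. The check has two steps.

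**Step 1: unit conversion.** Inputs: the limit of 1.5 mmol/L (Protocol synopsis and section 4.2), the molar mass of magnesium (24.305 g/mol) and its valence of 2.

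- 1.5 mmol/L × 24.305 mg/mmol = 36.46 mg/L = 3.65 mg/dL.
- 1.5 mmol/L × 2 = 3.0 mEq/L.
- In the other direction, 1.5 mg/dL = 15 mg/L ÷ 24.305 = 0.62 mmol/L, and 1.5 mEq/L ÷ 2 = 0.75 mmol/L.

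The last line only shows how much the meaning of the number depends on its unit. Neither value is put forward as the right limit.

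**Step 2: share of candidates below 1.5 mmol/L.** The documents give no reference range. Assumption: adult serum magnesium is roughly normal, with a central 95% range from L to U. Then mean = (L + U)/2, SD = (U − L)/(2 × 1.96), and the excluded share is Φ((1.5 − mean)/SD).

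| Assumed range (mmol/L) | Mean | SD | Share below 1.5 | Expected at or above 1.5, out of 256 |
|---|---|---|---|---|
| 0.65-1.05 | 0.85 | 0.102 | > 0.99999 | < 0.001 |
| 0.70-1.10 | 0.90 | 0.102 | > 0.99999 | < 0.001 |
| 0.75-1.02 | 0.885 | 0.069 | > 0.99999 | < 0.001 |
| 0.60-1.20 (deliberately wide) | 0.90 | 0.153 | 0.99996 | 0.01 |

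For the widest range, (1.5 − 0.90)/0.153 = 3.92, which gives 0.99996; 256 × (1 − 0.999956) = 0.01.

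A harsher grid used means from 0.8 to 1.2 and SDs from 0.10 to 0.20 mmol/L. The excluded share ran from 93.3% to 100%. The lowest value comes from mean 1.2 and SD 0.20, where (1.5 − 1.2)/0.20 = 1.5 and Φ(1.5) = 0.933. That case implies a central range of 1.2 ± 1.96 × 0.20, or 0.81 to 1.59 mmol/L, so its upper limit is already above 1.5. Even there, only about 256 × 0.067 = 17 of 256 would pass. Under a symmetric model, the mean itself would have to reach 1.5 mmol/L before half of candidates passed.

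Set against these results, enrolment of nearly 256 is hard to reconcile with literal use of the limit.

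**The case against.** The strongest objection is that the decisive premise lies outside the documents. The synopsis and section 4.2 agree with each other, and nothing in either document contradicts 1.5 mmol/L directly. That is correct, and the range must be labelled as an assumption. The conclusion hardly depends on it, however: any range whose upper limit is well below 1.5 gives the same answer. The heading of the item and the enrolment figure point the same way. The criterion speaks of an uncorrected imbalance, which could admit candidates whose value was raised before randomisation. No such step is described, and under the assumption nearly everyone would have needed it.

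A reader might also infer four stronger things that the documents do not support.

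- *The unit is wrong.* The number could equally be wrong. The documents show only that the two do not fit.
- *Truly low magnesium goes unscreened.* The literal text does exclude such candidates, since they too are below 1.5. Exclusion (16) also lets the investigator exclude anyone judged unsuitable. How sites screened magnesium in practice is not documented.
- *Sites are known to have ignored the limit.* This is inferred from enrolment. No screening values or eligibility checks are in the documents.
- *The PPS becomes arbitrary or nearly empty.* The PPS removes only major deviations that could affect evaluation of the primary endpoint, and neither document says that a breach of (12) is one. Protocol section 10.1 has a data review meeting settle the analysis populations before lock, and section 3.3.4 places final unblinding after that. The decision can therefore be made blind.

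It is also fair to say that, with enrolment nearly complete, a correction would change few if any screening decisions. Its value is mainly in the record.

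**Conclusion.** The concern holds in this form: the number and unit of the magnesium limit do not fit together in either place where it appears. Under the assumed adult ranges, more than 99.9% of candidates would meet the exclusion, and 93% or more under the harsher grid. With nearly 256 enrolled, the limit was probably not applied as written, and on the literal text nearly all randomised participants would be eligibility deviations. This describes a literal reading and is not an observed count.

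The effect on the analysis is limited. The FAS definition does not depend on eligibility, so the primary analysis is unaffected. The PPS sensitivity analysis changes only if a breach of (12) is classed as major. The conclusion rests on one assumption from outside the documents, namely that the usual adult range ends well below 1.5 mmol/L.

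**What to change.** 1. Reconcile the number and unit of the magnesium limit in the Protocol synopsis and section 4.2 (12) with the source of the criterion and with the eligibility check actually used, and correct both places. No replacement limit is proposed here.
2. List screening magnesium, with its unit, for all randomised participants against the reconciled criterion, and mark missing values. The listing should rely on the flow table and its note 8, because the narrative list of screening tests in Protocol section 6.2.1 does not name electrolytes.
3. At the blinded data review before lock, record how criterion (12) is handled in the deviation classification and in PPS membership. That decision belongs to the review already planned in Protocol section 10.1 and SAP section 4.1.2.

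Cost: a short protocol amendment, which needs ethics committee review and approval under Protocol section 9.2, plus one listing and one entry in the data review record. Sample size and the primary analysis do not change.
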